### 10.2 Listings

Listing number	Title
16.2	PATIENS DATA LISTINGS
16.2.1	Discontinued patients
Listing 16.2.1.1	Screen failure patients and non-inclusion reasons – SCR
Listing 16.2.1.2	Patients' disposition – SAF
16.2.2	Protocol deviation for enrolled patients
Listing 16.2.2.1	Protocol deviations at inclusion for treated patients – SAF
Listing 16.2.2.2	Protocol deviations during study for treated patients – SAF
16.2.4	Demographic data and Baseline characteristics by patient (enrolled patients)
Listing 16.2.4.1.1:2	Demographic and baseline characteristics: SCR/SAF
Listing 16.2.4.2.1:2	History of studied disease – SCR/SAF
Listing 16.2.4.3. 1:2	Prior Anti-Cancer Therapy: Medication – SCR/SAF
Listing 16.2.4.4.1	Relevant Medical History and current Medical Conditions – SAF
Listing 16.2.4.5.1:2	CA-125 concentration at study entry and during screening period – SCR/SAF
Listing 16.2.4.6	Signs and symptoms at baseline – SAF
Listing 16.2.4.7	Serology – SCR/SAF
16.2.5	Compliance and study conduct data
Listing 16.2.5.1	TG4050 administration – SAF
Listing 16.2.5.2	TG4050 administration per patient – SAF
Listing 16.2.5.3	Delayed, cancelled or stopped administration of TG4050 (Listing) – SAF
Listing 16.2.5.4	Discontinuation of study treatment and study (Table) – SAF
Listing 16.2.5.5	Prior and concomitant medications (on or after D1) – SAF
Listing 16.2.5.6	Prior and concomitant medications (before D1) – SAF
Listing 16.2.5.7	Further anti-cancer therapies – SAF
16.2.6	Individual efficacy response data by patient (enrolled patients)
Listing 16.2.6.1	CA-125 concentration during treatment period – SAF
Listing 16.2.6.2	Failure to treat/provide – SCR
Listing 16.2.6.3	Objective tumor assessments by evaluation – SAF
Listing 16.2.6.4	Detailed tumor assessment – SAF
Listing 16.2.6.5	Time to measurable relapse / Time to Progressive Disease – SAF
16.2.7	Adverse event listings by patient
Listing 16.2.7.1	Adverse events – SAF
Listing 16.2.7.2	Adverse events related to TG4050 – SAF
Listing 16.2.7.3	Serious Adverse events before treatment – SAF
16.2.8	Listing of individual laboratory measurements by patient
Listing 16.2.8.1	Laboratory parameters – Hematology – SAF
Listing 16.2.8.2	Laboratory parameters – Biochemistry – SAF
Listing 16.2.8.3	Other Laboratory parameters – SAF
Listing 16.2.8.4.1:2	Molecular Characterization tests – SCR/SAF
Listing 16.2.8.5	Vital Signs and, physical examination – SAF
Listing 16.2.8.6	Electrocardiogram and ECOG PS – SAF

Listing 16.2.9.1

Request for TG4050 manufacturing – [SCR](#)**11 REFERENCE**

Clopper, C. J., and Pearson, E. S. The Use of Confidence or Fiducial Limits Illustrated in the Case of the Binomial, *Biometrika* 1934;26,404–413

## 12 APPENDIX

### 12.1 Appendix 1 – Protocol deviations

Anticipated but not limited deviations for eligibility criteria are:

#### Screening period:

Category	Period	Deviation Code	Standard name of the deviation	Criticality
Inclusion criteria	Screening	INC01	Written informed consent not signed in accordance to ICH-GCP and national/local regulation before any protocol-related procedures that are not part of normal patient care	Major
Inclusion criteria	Screening	INC02.01	Male patients	Major
Inclusion criteria	Screening	INC02.02	Patients < 18 years of age	Major
Inclusion criteria	Screening	INC03.01	Histologically not confirmed high grade, stage IIIC or stage IVA serous ovarian, fallopian or primary peritoneal carcinoma	Major
Inclusion criteria	Screening	INC03.02	High grade, stage IIIC or stage IVA serous ovarian, fallopian or primary peritoneal carcinoma with normal CA-125 diagnosis	Major
Inclusion criteria	Screening	INC04	Patients have not undergone primary debulking surgery or not completed standard first-line platinum-based chemotherapy (at least 5 cycles of taxane-platinum combination) for whom tumor tissue has been banked from previous abdominal debulking surgery	Major
Inclusion criteria	Screening	INC05.01	Patients have not achieved a complete response to therapy, as demonstrated by no residual disease on most recent CT scan	Major
Inclusion criteria	Screening	INC05.02	Patients have CA-125 increasing by > 25% and > 10 UI/mL from nadir	
Inclusion criteria	Screening	INC06	Patient doesn't remain disease-free during at least 6 months after last dose of cytotoxic chemotherapy (maintenance therapy with bevacizumab or a PARP inhibitor is allowed)	Major

Inclusion criteria	Screening	INC07	No tumor tissue and peripheral blood samples available for exome and transcriptome sequencing	Major
Exclusion	Screening	EXCL01.1	Patient having received neoadjuvant chemotherapy prior to debulking surgery	Major
Exclusion	Screening	EXCL01.2	Patient having received cancer immunotherapy including cancer vaccines, any antibody/drug targeting T cell co-regulatory proteins such as anti-PD1, anti PDL1 or anti CTLA-4	Major
Exclusion	Screening	EXCL02	Patients with other active malignancy $\leq$ 3 years prior to registration except non-melanoma skin cancer, stage 0 in situ carcinoma and recent early stage papillary thyroid cancer are excluded. If there is an history of prior malignancy, patients must not be receiving other specific treatment for their cancer	Major
Exclusion	Screening	EXCL03	Patient post-organ transplantation, including allogeneic stem cell or bone marrow transplantation. History of blood transfusion within 3 weeks prior to study entry visit	Major
Exclusion	Screening	EXCL04	Known history of positive testing for Human Immunodeficiency Virus (HIV) or known AIDS (Acquired Immune Deficiency Syndrome)	Major
Exclusion	Screening	EXCL05	Any known allergy or reaction to eggs or attributed to compounds of similar chemical or biological composition to therapeutic vaccines/immunotherapeutic products	Major
Exclusion	Screening	EXCL06	Positive serology for Hepatitis C Virus (HCV) or positive serum Hepatitis B surface antigen (HBsAg) within 3 months prior to or at study entry (tests required)	Major

**Treatment period:**

Category	Period	Deviation Code	Standard name of the deviation	Criticality
Inclusion criteria	Treatment	INC08	If required, new ICF not signed before started treatment	Major
Inclusion criteria	Treatment	INC09	Eastern Cooperative Oncology Group (ECOG) performance status > 1 at treatment period initiation	Major
Inclusion criteria	Treatment	INC10	Patients who have not developed an asymptomatic relapse as defined by CA-125 > 2 times ULN on 2 occasions at least 1 week apart (GCIG criteria) or low volume radiological disease and CA-125 > ULN. Low volume radiological disease is defined as radiologically visible disease excluding intra-hepatic or splenic metastases, ascites or pleural effusion thought to require drainage	Major
Inclusion criteria	Treatment	INC11	Inadequate hematological, hepatic, and renal functions: 
 
○ Hemoglobin < 9.0 g/dL
 
○ Neutrophils count < 1.5 x10^9/L
 
○ Lymphocytes count < 0.9 x10^9/L
 
○ Platelets count <100 x10^9/L
 
○ Total bilirubin > 1.5 x ULN (except for patients with Gilbert's syndrome)
 
○ Aspartate aminotransferase (AST) > 2.5 x ULN
 
○ Calculated creatinine clearance < 45 mL/min using the Cockcroft & Gault formula or < 45 mL/min/1.73m^2 using other methods
 
	Major
Inclusion criteria	Treatment	INC12	Patients who received standard maintenance therapy within 30 days prior to TG4050 treatment (or within 14 days for PARP inhibitor)	Major
Exclusion criteria	Treatment	EXCL07	Measurable disease according to RECIST 1.1	Major

Exclusion criteria	Treatment	EXCL08	Major surgery within 4 weeks prior to treatment start	Major
Exclusion criteria	Treatment	EXCL09	Treatment with another investigational agent within 30 days prior to TG4050 treatment initiation	Major
Exclusion criteria	Treatment	EXCL10	Patients under chronic treatment with systemic corticosteroids or other immunosuppressive drugs for a period of at least 4 weeks and whose treatment was not stopped 4 weeks prior to TG4050 treatment initiation planned date, with the exception of patients with adrenal insufficiency who may continue corticosteroids at physiological replacement dose, equivalent to $\leq$ 10 mg prednisone daily. Steroids with no or minimal systemic effect (topical, inhalation) are allowed.	Major
Exclusion	Treatment	EXCL11	Vaccination for the prevention of infectious diseases with a live vaccine during the four-week period prior to TG4050 treatment initiation planned date. Furthermore, patients should not receive any live vaccine during the period of study treatment administration	Major
Exclusion	Treatment	EXCL12	Patients with any underlying medical condition, that in the opinion of the investigator, could make the patient inappropriate for entry into this study or interfere significantly with the proper assessment of safety or toxicity of the study treatment	Major
Exclusion	Treatment	EXCL13	Uncontrolled intercurrent illness including, but not limited to ongoing or active infection, symptomatic congestive heart failure, unstable angina pectoris, cardiac arrhythmia or psychiatric illness/social circumstances that could limit compliance with study requirements	Major
Exclusion	Treatment	EXCL14	History of myocardial infarction $\leq$ 6 months	Major

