**Treatment period:**

8. Eastern Cooperative Oncology Group (ECOG) performance status of 0 or 1 at treatment period initiation.
9. Patients who have developed an asymptomatic relapse as defined by:
  - Cohort A: CA-125  $\geq$  2 times Upper Limit of Normal (ULN) on 2 occasions at least 1 week apart (GCIG criteria) or low volume radiological disease and CA-125  $>$  ULN. Low volume radiological disease is defined as radiologically visible disease excluding intra-hepatic or intra-splenic metastases, ascites or pleural effusion thought to require drainage
  - Cohort B: patient asymptomatic with measurable disease excluding intra-hepatic or splenic metastases, ascites or pleural effusion thought to require drainage, whatever serum CA-125 level and for whom further treatment is not planned within 2 months. Longest diameter of measurable lesion on CT-scan must not exceed 2 cm for non-nodal lesions and 2.5 cm in short axis for nodal lesions
10. Adequate hematological, hepatic and renal functions:
  - Hemoglobin  $\geq$  9.0 g/dL
  - Neutrophils count  $\geq$  1.5  $\times$  10^9/L
  - Lymphocytes count  $\geq$  0.9  $\times$  10^9/L
  - Platelets count  $\geq$  100  $\times$  10^9/L
  - Total bilirubin  $\leq$  1.5  $\times$  ULN (except for patients with Gilbert's syndrome)
  - Aspartate aminotransferase (AST)  $\leq$  2.5  $\times$  ULN
  - Calculated creatinine clearance  $\geq$  45 mL/min using the Cockcroft-Gault formula or  $\geq$  45 mL/min/1.73m^2 using other methods

Note: for Cockcroft-Gault formula:

$$\text{Creatinine clearance for females (mL/min)} = \frac{(140 - \text{age})(\text{weight in kg})(0.85)}{(72)(\text{serum creatinine in mg/dL})}$$

$$\text{Creatinine clearance for females (mL/min)} = \frac{(140 - \text{age})(\text{weight in kg})(1.04)}{(\text{serum creatinine in } \mu\text{mol/L})}$$

11. Patients who received standard maintenance therapy will stop before initiation of TG4050 administration. A free interval of at least 30 days will be respected before first dosing of TG4050 except for PARP inhibitors (at least 14 days).

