### Treatment period

7. Measurable disease associated with the appearance of symptoms justifying initiation of further treatment.
8. Major surgery within 4 weeks prior to treatment start
9. Treatment with another investigational agent within 30 days prior to TG4050 treatment initiation.
10. Patients under chronic treatment with systemic corticosteroids or other immunosuppressive drugs for a period of at least 4 weeks and whose treatment was not stopped 2 weeks prior to TG4050 treatment initiation planned date, with the exception of patients with adrenal insufficiency who may continue corticosteroids at physiological replacement dose, equivalent to  $\leq$  10 mg prednisone daily. Steroids with no or minimal systemic effect (topical, inhalation) are allowed.
11. Vaccination for the prevention of infectious diseases with a live vaccine during the four-week period prior to TG4050 treatment initiation planned date. Furthermore, patients should not receive any live vaccine during the period of study treatment administration.
12. Patient with any underlying medical condition that, in the opinion of the investigator, could make the patient inappropriate for entry into this study or interfere significantly with the proper assessment of safety or toxicity of the study treatment.
13. Uncontrolled intercurrent illness including, but not limited to, ongoing or active infection, symptomatic congestive heart failure, unstable angina pectoris, cardiac arrhythmia, or psychiatric illness/social situations that would limit compliance with study requirements.
14. History of myocardial infarction  $\leq$  6 months.

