#### 2.1.2 Treatment period

A treatment period with TG4050 monotherapy will start in:

- Cohort A: when patients develop an asymptomatic relapse defined on the basis of progressive serial elevations of serum CA-125 (GCIG criteria) or documentation of low volume radiological disease with CA-125 > ULN. Low volume radiological disease is defined as radiologically visible disease excluding intra-hepatic or intra-splenic metastases, ascites or pleural effusion thought to require drainage.
- Cohort B: when patients develop an asymptomatic relapse with measurable disease excluding intra-hepatic or intra-splenic metastases, ascites or pleural effusion thought to require drainage, whatever serum CA-125 level and for whom further treatment is not planned within 2 months. Longest

diameter on CT-scan must not exceed 2 cm for non-nodal lesions and 2.5 cm in short axis for nodal lesions.

Patients will receive TG4050 up to a total of 20 injections or until documented disease progression as defined by RECIST 1.1 justifying treatment with chemotherapy, or unacceptable toxicity including occurrence of a dose-limiting toxicity, or patient withdrawal for any reason, whichever occurs first.

All treated patients will be followed for:

- Safety assessments performed on a weekly basis for the first 6 weeks and every 3 weeks thereafter.
- Serum CA-125 levels assessed in an accredited central laboratory within 7 days prior to treatment initiation and every 3 weeks after start of study treatment.
- Imaging performed within 21 days prior to treatment initiation, at day 43 and every 9 weeks after study treatment start.
- Immune responses evaluated in the blood at baseline and on days 8, 22, 43, 64, 85 and 211; in the tumor at the time of documented disease progression according to RECIST 1.1.

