### **8.3.8 CA-125 serum concentration in blood**

CA-125 serum concentration in blood will be analyzed centrally (normal ranges 0 to 35 U/mL). Data related will be listed. If data are collected and recorded in eCRF, all data will be pooled and in case of data available at the same date locally and centrally, priority will be given to central data.

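### SAP Appendix 1 grades as major deviations two features that the protocol accepts: asymptomatic measurable disease, and neoadjuvant chemotherapy with interval debulking

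*SAP*

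**What the plan says.** SAP 12.1 (Appendix 1) gives each eligibility deviation a code and a criticality. In the treatment-period table, EXCL07 reads in full "Measurable disease according to RECIST 1.1" and is graded Major. INC10, also Major, covers patients without an asymptomatic relapse "as defined by CA-125 > 2 times ULN on 2 occasions at least 1 week apart", or by low volume radiological disease with CA-125 above ULN. Those are the Cohort A rules; Cohort B is not mentioned. In the screening table, EXCL01.1 is "Patient having received neoadjuvant chemotherapy prior to debulking surgery", and INC04 covers patients who did not have primary debulking. Both are Major.

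The protocol reads differently. Section 4.1, criterion 9 admits "Cohort B: patient asymptomatic with measurable disease excluding intra-hepatic or splenic metastases", subject to lesion size limits and to no further treatment being planned within 2 months. SAP 2.1.2 carries the same cohort: "Cohort B: when patients develop an asymptomatic relapse with measurable disease excluding intra-hepatic or intra-splenic metastases". Protocol 4.2, exclusion 7 is narrower than EXCL07: "Measurable disease associated with the appearance of symptoms justifying initiation of further treatment". Protocol criterion 4 accepts primary or interval debulking. Criterion 7 says which tissue to use when the patient had neoadjuvant chemotherapy, and section 4.2 contains no neoadjuvant exclusion.

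Protocol 9.6 leaves the list of major deviations to the SAP as the means of fixing the evaluable population. SAP 6.2 removes every patient with a major deviation from the EPP, and SAP 8.5.2 counts such patients by type and overall. SAP 1 names protocol Version 9.0 as its source.

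**The concern.** The appendix grades as major what the protocol permits. Every correctly enrolled Cohort B patient has measurable disease and so meets EXCL07. Every patient who had neoadjuvant chemotherapy followed by interval debulking meets EXCL01.1, and meets INC04 because she had no primary debulking.

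What is at stake is the account of eligibility compliance. Protocol 6.2.1 states that a deviation from any eligibility criterion keeps a patient out of the treatment period. A false Major flag would therefore report that a properly enrolled patient in a first-in-man study should not have been treated. It would appear in Tables 14.1.1.3 (SCR) and 14.1.1.4 (SAF) and in Listing 16.2.2.1. It would also lower the EPP count, which may be shown in Table 14.1.1.2.

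**Working it through.** The plan states no figure on this point, so there is nothing to reproduce. The check sets the texts side by side and then works out the possible size.

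**Codes that carry the two main conflicts**

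| SAP code | Appendix 1 rule | Protocol rule | Eligible patients flagged as printed |
|---|---|---|---|
| EXCL07 | Any RECIST-measurable disease | Exclusion 7: only with symptoms that call for further treatment; criterion 9 admits Cohort B | All of Cohort B; any Cohort A patient with a measurable lesion |
| INC10 | Cohort A relapse rules only | Criterion 9 has a Cohort B branch, whatever the CA-125 | Cohort B patients whose CA-125 is not above ULN (a second code) |
| EXCL01.1 | Neoadjuvant chemotherapy before debulking | Criterion 7 provides for it; no exclusion in 4.2 | All who had neoadjuvant chemotherapy |
| INC04 | No primary debulking | Criterion 4 accepts interval debulking | All who had interval debulking only |

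Cohort A appears under EXCL07 because of how the protocol defines its imaging route: "Low volume radiological disease is defined as radiologically visible disease excluding intra-hepatic or intra-splenic metastases", ascites or effusion needing drainage. Nothing there limits it to non-measurable lesions.

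**Codes with smaller differences**

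- INC03.01 and INC03.02 say stage IVA; protocol criterion 3 says stage IV. As printed, INC03.01 also flags an eligible stage IV patient who is not IVA.
- INC10 uses a strict inequality for CA-125, while the protocol uses at least 2 times ULN. With "normal ranges 0 to 35 U/mL" in SAP 8.3.8, 2 × 35 = 70 U/mL, so the two rules part only at exactly 70. INC10 is already counted above.
- INC05.02 tests a rise of more than 25% and more than 10 units from nadir; protocol criterion 5 asks for a normal value. From any nadir below 35 − 10 = 25 U/mL, a rise can meet the code (25% of 25 is 6.25, so the 10-unit limb decides) and still end inside the normal range. Its criticality cell reads blank, which may come from the text extraction.
- EXCL10 and protocol exclusion 10 give different intervals for stopping corticosteroids or immunosuppressants (4 weeks and 2 weeks).

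**Count of codes.** Screening has 10 inclusion and 7 exclusion codes; treatment has 5 and 8. 10 + 7 + 5 + 8 = 30, of which 29 read Major and 1 (INC05.02) reads blank. Four codes carry the main conflicts (EXCL07, INC10, EXCL01.1, INC04) and four the smaller ones (INC03.01, INC03.02, INC05.02, EXCL10).

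**Size in the SAF.** SAP 4 gives 6 treated patients. Neither document gives their split by cohort, lesion type or neoadjuvant treatment, so the number falsely flagged, k, is an assumption between 0 and 6. The rate rises by up to k/6, and the EPP holds at most 6 − k:

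- k = 1: 1/6 = 16.7%, EPP at most 5
- k = 2: 2/6 = 33.3%, EPP at most 4
- k = 3: 3/6 = 50.0%, EPP at most 3
- k = 6: 6/6 = 100%, EPP at most 0

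These are upper values, because a flagged patient may also have a true major deviation or fewer than 6 injections.

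**Size in the SCR.** Each false flag adds up to 100/N points. The final N is not given. At the planned 60 this is 100/60 = 1.7 points; at an assumed 30 it is 100/30 = 3.3. For patients never treated, only the screening-period codes are relevant.

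**The case against.** The strongest reply is that Appendix 1 is a dictionary of standard names and not a flagging rule. The SAP calls it non-exhaustive, and SAP 8.5.1 summarises deviations from the protocol's eligibility criteria as collected in the eCRF. A patient who meets the protocol then has nothing to code. This stands as a limit: the wording conflict is certain, but its effect on counts is conditional, because the eCRF coding is not visible and part of SAP 6.2 is redacted. It does not remove the fault. A non-exhaustive list can be added to, but that does not cancel the codes it prints, and protocol 9.6 relies on this list.

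Second, little depends on it. The document history says EPP tables and listings were removed, the listed safety and efficacy outputs use the SAF, and the data review meeting in SAP 7.2 could catch the error. An EPP line in Table 14.1.1.2 is inferred from SAP 8.2.2, which asks for exclusions from populations with reasons but names only the SAF count. All of this is right, and it bounds the harm.

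Third, Cohort A may have been meant to exclude measurable disease, since its endpoint is time to measurable relapse and SAP 7.6.1 and 8.8 discuss response in non-measurable lesions. That is a fair reading of intent, but the entry definition does not say it. The Cohort B conflict does not depend on it.

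Fourth, the neoadjuvant conflict rests mainly on the protocol. SAP 8.3.6 offers neoadjuvant as a prior-therapy setting, but a generic category list would do so anyway. That is fair, and the protocol text is enough.

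Finally, some patients may have entered under other protocol versions. The documents do not show this, and SAP 1 cites Version 9.0 only.

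**Conclusion.** The concern holds. Appendix 1 contradicts protocol 4.1 and 4.2 on both features, and on measurable disease it also contradicts SAP 2.1.2. If the codes are applied as printed, eligible patients are reported as major deviators and leave the EPP. The number is between 0 and 6 of the 6 treated and cannot be narrowed from the documents; each false flag is worth up to 16.7 percentage points in the SAF. The primary safety results and the listed efficacy outputs are not affected. The harm is a wrong account of eligibility compliance and possibly a wrong EPP count. It should be fixed, since the conflict is plain and the correction is cheap.

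**What to change.** Before lock, align EXCL07, INC10, EXCL01.1, INC04, INC03.01, INC03.02 and INC05.02 line by line with protocol 4.1 and 4.2. In particular:

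- Restrict EXCL07 to what protocol exclusion 7 bars.
- Give INC10 a Cohort B branch and the protocol's CA-125 inequality.
- Remove the neoadjuvant code and admit interval debulking in INC04.
- State the criticality of INC05.02.
- Reconcile EXCL10 with protocol exclusion 10; this review takes no position on the interval.

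Then re-derive the deviation flags and the EPP count, and check Tables 14.1.1.2 to 14.1.1.4 and Listing 16.2.2.1 against them. The cost is a revision of the SAP appendix and, where the codes are already programmed, a rerun of the derivation. No patient is affected.
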